### IV. Administrative Organization

This study involves collaboration among investigators and support staff from the School of Nursing, the Department of Medicine, Hematology/Oncology and Public Health Sciences divisions, the Cardinal Bernadin Cancer Center, the Loyola University Medical Center (LUMC) Pharmacy and the Clinical Research Office (CRO). This investigation will be conducted on the Loyola University Health Sciences Campus. Participants will be evaluated in the Bernadin Cancer Center and in a devoted research space within the Maguire Building utilizing the nursing expertise offered by the School of Nursing research staff.

Laboratory analyses will be completed in the Core Laboratory of LUHS, within a Basic Science Laboratory at LUHS and/or outsourced to Quest Diagnostics. Biospecimens will be stored in the biorepository supported by the CRO (LU# 204853). Additionally, the CRO will offer biostatistical support, data management oversight and regulatory services required for this trial. The LUMC Pharmacy will provide and dispense the study medication and the Public Health Science division will provide the machinery and technical expertise for body composition assessment. Because participants may be referred from surrounding oncologists, this study will leverage existing relationships among investigators to promote collaborations across institutions. The investigators on this study reflect a multidisciplinary team with expertise in medicine, nutrition, nursing, oncology, biostatistics, and public health.

## **V. Study Design**

**a. Research design:** This study is comprised of an intervention arm (Group 1) and non-intervention arm (Group 2). For eligible women with low serum levels of vitamin D, we propose an 8 week open label, single arm “proof of concept” study to address concerns regarding vitamin D3 dosing, to monitor important laboratory parameters and to assess potential effects on short-term outcomes. While a randomized controlled trial (RCT) has been the traditional model to evaluate the efficacy of vitamin D supplementation, this design may be considered premature until the safety of this therapy has been evaluated in a patient population with the potential for high clinical acuity. For the women who meet all eligibility criteria except they have normal serum levels of vitamin D (Group 2), we will assess their symptomology and test associations with the biomarkers of inflammation.

**b. Study population:** Adult females with ER+ MBC can participate in the present study provided they are under the care of medical oncologist and meet all eligibility criteria. Women with early stage disease (Stages 0-3) or women with MBC who are ER- are unable to participate in this study.

**c. Sample size and power considerations:** Because this is a pilot project that will assess the feasibility, preliminary safety and short-term efficacy of a vitamin D3 intervention in this population, typical sample size calculations will not be employed. We will assess symptoms at baseline for all participants to establish prevalence estimates and at three time points in the intervention group to help increase our abilities to detect changes over time. Because of the high prevalence of vitamin D deficiency among breast cancer survivors (~75%) and the high volume of patients seen at LUMC and by [name] (collaborator), we anticipate that we can successfully recruit and enroll 50 women who meet the eligibility criteria. Our goal is to recruit 25 women for the intervention arm. Factoring in an attrition rate of ~20%, we should have complete data on 20 women who complete the intervention. This sample size is sufficient to demonstrate feasibility and will allow for the generation of effect size and variance estimates, as well as confidence interval widths around these estimates for future applications.

**d. Study endpoints:** The primary endpoint in this study is serum 25(OH)D. We will use this serum biomarker to assess if repletion levels are obtained ( $\geq 30$  ng/dl), to test associations with symptoms and/or to assess the degree of change from baseline to follow up. Serum calcium and serum estradiol levels will be monitored to be sure these levels normalize or to assess clinically significant changes following supplementation, respectively.

To address our secondary endpoints, we will be assessing symptoms, including pain (Brief Pain Inventory; Cleeland, 1994; FACT-Bone pain, Broom, 2009), fatigue (Piper Fatigue Scale; Piper, 1998), mood (Hospital Anxiety and Depression Scale; Herrmann, 1997; Patient Health Questionnaire-8; Kroenke, 2001), muscle function (handgrip strength), sleep (Pittsburg Quality Sleep Index; Carpenter, 1998), overall health and QOL (FACT-B; Brady, 1997; FACT-ES; Fallowfield, 1999.) These specific tools were selected because they have been utilized in breast cancer populations and/or other cancer populations and will provide the ability to compare our findings to others. In addition, to address important confounders, we will gather data on diet (Block Calcium/Vitamin D screener; Cummings, 1987), physical activity (Godin Leisure Time Activity, 1985), body composition (bioelectrical impedance, dual energy x-ray

absorptiometry), sunlight exposure (Glanz sunlight exposure, 2008), social support (Multiple Outcomes Social Support; Sherbourne, 1991) and previous/current breast cancer treatments.

## **VI. Study Procedures**

**a. Study subject procedures:** Subjects must meet all of the inclusion and none of the exclusion criteria to be enrolled into the intervention arm of the study. In addition, women meeting all of the inclusion and exclusion criteria except the serum 25(OH) cut point will be offered the opportunity to participate in the cross-sectional arm of the study.

i. The following criteria will be used to assess eligibility and participation.

### Inclusion Criteria:

1. Metastatic breast cancer (Stage IV)
2. Histologically confirmed estrogen receptor positive disease
3. Female
4. Serum 25(OH) <30 ng/ml
5. Age  $\geq$  18 years
6. Pre or post-menopausal
7. ECOG Performance status 0-2
8. Adequate organ function as defined as GFR > 30 mls/min and serum calcium  $\leq$  10.4 mg/dl
9. Any race/ethnicity
10. English speaking
11. No changes to MBC treatments within 30 days of enrollment and/or deemed clinically stable by their treating physician
12. Willingness to sign a written informed consent and complete questionnaires
13. Cease ingestion of vitamin D supplementation not study related

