b. MBC and vitamin D: Low levels of serum 25(OH)D at the time of diagnosis have been shown to predict recurrence and death, underscoring the clinical significance of widespread vitamin D deficiency/insufficiency reported among breast cancer survivors. Purportedly 1,25 (OH)2D has been shown to induce cell-cycle arrest, increase expression of receptor activator of nuclear factor κB ligand, and down regulate the expression of cyclooxygenase-2. Hence, sufficient levels of vitamin D are needed to favorably impact breast cancer biology. In women previously diagnosed and treated for breast cancer, the prevalence of vitamin D deficiency/insufficiency is ~75%, yet these studies predominantly focused on women with early disease (Stage I-III). Vitamin D studies conducted in women with MBC are limited, but report similar prevalence estimates with lower overall levels of serum vitamin D.

[figure not shown]
c. Breast cancer treatment and symptom management: For women with estrogen receptor positive (ER+) disease, aromatase inhibitors are considered a frontline therapy, since they efficiently and effectively decrease circulating estrogen by halting the conversion of androgens to estrogen. Unfortunately, arthralgias and myalgias are highly prevalent within weeks of initiation and may result in discontinuation. The etiology of these musculoskeletal disturbances is not well understood; however, it has been postulated that estrogen itself has analgesic properties and that cytokines, such as IL-1, TNF-α, are suppressed with higher levels of estrogen. It has been further suggested that cartilage turnover increases as estrogen decreases, and that the combination of efficient estrogen deprivation combined with low serum 25(OH)D accentuates muscle and joint pain. Thus, low levels of estrogen are associated with reduced pain tolerance and increased inflammation. Additionally, breast cancer treatment is accompanied by a myriad of endocrine symptoms, including weight gain, fatigue and mood swings. In non-breast cancer populations, vitamin D supplementation has been shown to regulate weight, mood and to decrease inflammation.

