### III. Study Aims

Several clinical trials are underway to investigate if vitamin D2 or D3 provided at various doses (10,000-50,000 IUs/week) can improve the side-effects associated with anti-estrogen therapies, specifically aromatase inhibitors (AIs). However, these current trials use variable forms of vitamin D and predominantly include women with Stage I-III disease, excluding women with metastatic breast cancer. Evaluation of the safety of vitamin D3 supplementation is crucial since supplementation can lead to hypercalcemia and importantly, *in vitro* studies have shown that vitamin D3 influences the transcription of a gene that increases estrogen production. To assure that vitamin D3 does not abrogate the clinical effects of anti-estrogen therapies, the effect of vitamin D3 supplementation on estrogen production requires evaluation. Therefore, the overarching goal of this pilot study is to evaluate the safety, feasibility and efficacy of vitamin D3 supplementation in women with MBC. We will address and test the following aims and hypotheses, respectively:

**Aim 1:** To determine if weekly supplementation of 50,000 IUs of vitamin D3 raises serum levels of 25(OH)D to >30 mg/dl without adverse effects.

**Hypothesis 1:** Women who are compliant with vitamin D3 supplementation, as evidenced by normalization (>30 mg/dl) or increases in their serum 25(OH)D levels, will not experience significant changes in serum calcium or serum estradiol levels.

**Aim 2:** To determine the effect of vitamin D3 supplementation on symptom management.

**Hypothesis 2:** Women who achieve serum concentrations of 25 (OH)D ≥30 mg/dl or experience significant increases in 25(OH)D will exhibit improvements in pain, fatigue, sleep, mood, muscle function and overall quality of life.

**Exploratory Aim:** To explore the mechanistic effects of serum vitamin D levels and vitamin D3 supplementation on inflammatory markers and potential associations with symptom management.

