*Sun exposure:* Because sunlight constitutes the major source of vitamin D, the adult sun habits questionnaire by Glanz et al will be used. Two questions inquiring about summer sun exposure will be used quantify time spent in the sun, which directly correlates with serum vitamin D levels.

*Godin Exercise Leisure-time Questionnaire:* This 4-item tool allows for the quick quantification of time spent engaged in strenuous, moderate or light activities over a typical 7-day period showing reliability coefficients of 0.8 with  $\dot{V}O_2$  measures. A weekly leisure activity score is generated, as well as the frequency of leisurely activities. This tool is recommended and made available by the NCI.

*Medical Outcomes Study Social Support Survey:* The self-administered survey is a 19-item multi-dimensional scale assessing four aspects of social support: tangible support, affectionate, positive social interaction and emotional/informational support (Cronbach’s alphas >0.9 for all subscales.) Total and subscale scores are obtained and compared, with higher scores indicating more support.

**ix. Study completion:** Participants in the intervention will return to LUMC after 8 weeks of supplementation for their final blood analyses (serum 25(OH)D, calcium, , serum estradiol, inflammatory markers), anthropometric and body composition evaluations, pill counts and questionnaire completion. An 8 week intervention was selected because: 1) this timeframe is consistent with the clinical practice guidelines of the Endocrine Society for vitamin D repletion, and 2) it is an efficient and opportune time to assess the effects of vitamin D on biological and symptom outcomes. Participants in the non-intervention arm will not be followed after their baseline visit. They will be considered “complete” after their baseline visit.

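### Inclusion item 11 lets a physician's statement of stability stand in for the 30-day no-change rule, so drift from a recent endocrine treatment change can be mixed into the uncontrolled estradiol and symptom results

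*Protocol*

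**What the plan says.** Protocol section VI.a.i, inclusion item 11, sets the treatment-stability rule: "No changes to MBC treatments within 30 days of enrollment and/or deemed clinically stable by their treating physician". Section VI.a introduces the list with "Subjects must meet all of the inclusion and none of the exclusion criteria to be enrolled into the intervention arm of the study", so item 11 must be met, but its wording allows either limb to meet it. Clinical stability is not defined, and no exclusion criterion names a recent change of endocrine therapy.

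The background (section II.c) says of aromatase inhibitors that "they efficiently and effectively decrease circulating estrogen by halting the conversion of androgens to estrogen", and that "arthralgias and myalgias are highly prevalent within weeks of initiation and may result in discontinuation".

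Hypothesis 1 (section III) predicts that compliant women "will not experience significant changes in serum calcium or serum estradiol levels". Table 1 schedules estradiol at weeks 0 and 8, and pain at weeks 0, 4 and 8. Section V.a describes the intervention part as an "8 week open label, single arm" study. Section VI.a.ix adds: "Participants in the non-intervention arm will not be followed after their baseline visit".

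Laboratory change is tested with paired t tests and symptom change with repeated measures (protocol section VIII). The SAP reports Wilcoxon signed rank tests of change from baseline. Section V.d counts past and current cancer treatment among the important confounders, and Table 1 collects treatments at week 0. The adjustment list in the abstract (sunlight, diet, activity, body composition) leaves treatment out, and neither analysis section uses it.

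**The concern.** A before-and-after comparison without a control relies on participants being in a steady state at baseline. Item 11 is the eligibility rule meant to secure this for cancer treatment, and as worded its 30-day window need not bind anyone whose physician considers her stable. Clinical stability of disease is not the same as a settled hormone level or a settled symptom score.

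The overlap with the outcomes is direct. The protocol's safety worry is that vitamin D might raise estrogen. A woman who has just started an aromatase inhibitor would be expected, on the protocol's own account, to show falling estradiol and possibly new joint or muscle pain inside the 8 weeks. The first can hide an estradiol rise and so give false reassurance on safety. The second can hide a symptom benefit. Neither can be separated from a vitamin D effect using Group 1's average change alone.

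**Working it through.** **Inputs from the documents.** 25 women in Group 1 and about 20% attrition (section V.c); tests of change as above; p < 0.05 for significance and p < 0.10 for a trend (SAP). The plan's own figure reproduces: 25 x 0.80 = 20 completers. The documents give no estradiol mean, SD or margin, and no count of women with recent changes, so everything below is illustration on stated assumptions.

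**Illustration in pg/ml.** Assume that k of 20 completers started an aromatase inhibitor just before entry and fall from 20 to 2 pg/ml (change -18), while the other 20 - k truly rise by 2.

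Mean change = [2(20 - k) - 18k]/20 = 2 - k. At k = 3: (34 - 54)/20 = -1.0, against +2.0 if all 20 rose by 2.

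Paired t at k = 3: the sum of squared deviations is 17 x 3² + 3 x 17² = 153 + 867 = 1,020. SD = √(1,020/19) = 7.33, SE = 7.33/√20 = 1.64, t = -0.61, p about 0.55.

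Signed rank at k = 3: the 17 smaller changes share rank 9, so W+ = 17 x 9 = 153. The three larger share rank 19, so W- = 57. The expected value is 105. The tie-corrected variance is 717.5 - (4,896 + 24)/48 = 615, so z = 48/24.8 = 1.94 and p about 0.053, towards a rise. An exact sign-flip calculation gives about 0.06.

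Range over k:

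| Recent starters k | Mean change (pg/ml) | Paired t p | W+ / W- | Signed rank p (normal approx.) |
|---|---|---|---|---|
| 1 | +1.0 | 0.33 | 190 / 20 | 0.0004 |
| 2 | 0.0 | 1.00 | 171 / 39 | 0.007 |
| 3 | -1.0 | 0.55 | 153 / 57 | 0.053 |
| 4 | -2.0 | 0.29 | 136 / 74 | 0.22 |

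The mean and the t test are disturbed by a single woman. In this example the rank test holds up until about three.

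**A result that does not depend on the pg/ml values.** If the three largest absolute changes among 20 women are all falls, W- is at least 18 + 19 + 20 = 57. The two-sided 5% critical value at n = 20 is 52, so the signed rank test cannot show a significant rise, whatever the other 17 women do.

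**Simulation in SD units.** Two-sided signed rank test at 0.05, n = 20, 4,000 runs per setting, assumed true rise of 0.7 SD (change scores with SD 1). Each recent starter carries an added shift D, so the mean moves by kD/20.

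| k | D = -1 SD | D = -2 SD | D = -3 SD |
|---|---|---|---|
| 0 | 82% | 83% | 82% |
| 1 | 76% | 67% | 59% |
| 2 | 68% | 45% | 29% |
| 4 | 50% | 11% | 1% |
| 6 | 31% | 1% | 0% |

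Cells are the chance of detecting the rise; the differences in the k = 0 row are simulation noise. With no vitamin D effect and D = -2, the chance of a significant false fall goes from about 3% (k = 0) to 4%, 7%, 18% and 37% for k = 1, 2, 4 and 6.

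**Pain.** If three of 20 women worsen by an assumed 2 points on a 0-10 scale, the group mean moves by 3 x 2/20 = 0.3 points. One to six women give 0.1 to 0.6.

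**The case against.** The best defence is that the physician's judgement is a real filter. Staff also confer with the medical oncologist after the blood results (section VI.a.iv), and exclusion 13 leaves room for investigator discretion. Nothing in the documents shows that any recently changed woman was enrolled. This stands as a limit on how often the problem arises. It does not close the route, because none of these steps refers to a recent treatment change.

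A reader might go further than the documents allow in four ways.

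- **That the safety result changes sign.** In the illustration only the mean does so. The SAP's signed rank test still points to a rise at k = 3 and, at p about 0.053, would be labelled a trend. The paired t test at p about 0.55 shows no significant fall.
- **That the bias has a known direction.** That holds only for aromatase inhibitor starts. Item 11 covers any change of treatment, and the background itself says the symptoms may lead women to stop. By the same mechanism, stopping would raise estradiol and ease joint pain.
- **That the primary endpoint is compromised.** Section V.d names serum 25(OH)D, and nothing shows that a recent endocrine change affects it.
- **That individual safety monitoring fails.** Section VII.c takes a woman off study for a clinically significant estradiol increase. Falls in other women cannot hide a marked rise in her. Only her own recent start could.

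It is also fair to say that this is a pilot without a formal power calculation, and that the SAP is written in the past tense, so rewording item 11 cannot change who is in this dataset. The sensitivity analysis remains possible.

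**Conclusion.** The concern holds in a limited form. As worded, item 11 allows entry within 30 days of a treatment change, and neither the design nor the planned tests separate the resulting drift from a vitamin D effect. The exposed results are the group-level estradiol change in Aim 1 and the symptom changes in Aim 2.

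The size depends on how many such women there are, which the documents do not say. With one, the rank test is little affected in the pg/ml example, although the mean is halved. With three or more large falls among 20, a significant rise can no longer be shown. The effect is masking of a signal, with the direction set by the type of treatment change. The numbers of starters, the 20 to 2 pg/ml fall, the 2 pg/ml rise and the SD shifts are all assumptions. This is a cheap improvement to the secondary and safety reporting, not a flaw in the primary endpoint.

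**What to change.** 1. For the present data, flag each Group 1 woman whose cancer treatment changed in the 30 days before the baseline draw. Use the week 0 treatment history, and chart dates where the form lacks them: the protocol lists treatments but does not say that start or change dates are recorded. State the number flagged and the type of change, and report estradiol and symptom changes with and without these women.
2. For any further enrolment, or for the larger trial this pilot is meant to support, the sponsor should reconcile the two limbs of item 11 so that the protocol's own 30-day window binds, with both limbs required.

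The cost is some chart review for about 20 to 25 women and, under the second change, entry up to 30 days later for some women within a 12-month recruitment period. Neither step deals with women just past 30 days who are still changing, or with treatment changes during the 8 weeks. Recording treatment change dates through week 8 would at least make those visible.

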### Exclusion Criteria:

1. Women with Stage I-III breast cancer
2. Serum 25(OH)D levels  $\geq$  30 ng/ml
3. Untreated CNS involvement
4. History of kidney stones
5. History of renal failure
6. History of hyperparathyroidism
7. History of hypersensitivity to vitamin D
8. Non-English speaking
9. Currently pregnant or lactating, or anticipating pregnancy
10. Unwilling to cease ingestion of calcium supplements (>1000 mg/d)
11. Unwilling or unable to complete informed consent or study questionnaires
12. Psychiatric or other clinical conditions that preclude study compliance
13. Other important medical or safety considerations at the discretion of the investigator and/or study physician, including non-compliance with the study therapy or other activities

**ii. Recruitment sites and recruitment:** Women with MBC will be recruited from Cardinal Bernadin Cancer Center at LUMC with the direct assistance of the research nurses in the Breast Oncology Clinic

and support from the medical oncologists who treat these women. Participants will be informed of the study verbally and provided with a study brochure during their clinic appointment. Interested participants will be contacted by the study staff to explain the study in more detail and answer questions. In order to inform a broader sample of patients from LUMC about the study, we will send letters describing the investigation to the appropriate patients under the care of LUMC medical oncologists. An IRB approved waiver of HIPPA authorization will be used to identify patients from these physicians who meet the study criteria using CPT codes. We will provide flyers in the breast oncology clinic and surrounding clinics for potential participants to contact us. In addition, [name], a medical oncologist at Rush University Medical Center (RUMC), will verbally inform her patients about the study, provide handouts to those who express interest, and refer them to [name] for further evaluation. (Drs. [name] and [name] successfully collaborated on a previous pilot described in Preliminary work.) Women with confirmed interest will be screened via telephone to see if they can be scheduled to return to the research office for consent and baseline study assessment.

**iii. Initial screening:** Referred participants will be phoned or seen in clinic to describe the study. If interested, age, health information and questions regarding vitamin D supplementation will be asked. If any of the exclusion criteria are reported, they will not be able to continue their participation. If initially eligible, they will be scheduled for a blood draw.

**iv. Baseline screening and enrollment:** Interested participants will be consented by the PI or study nurse in a private room, assigned a unique study identification number and undergo phlebotomy. Participants will have their blood drawn in the Cardinal Bernadin Cancer Center Phlebotomy Laboratory to determine serum levels of vitamin D and other relevant laboratory values (Refer to Measurements.) Participants will in the non-intervention arm (Group 2) will be asked to complete the questionnaires, either in person, over the phone or via mail.) The research study staff will review the results of the serum vitamin D blood tests and confer with the medical oncologist regarding further participation in the study. Participants who are vitamin D deficient (<30 mg/dl) will return to LUMC to participate in the intervention arm (Group 1), to complete questionnaires and to receive the study medication.

**Optional Biobanking.** At the study completion visit, participants may *optionally* agree to reposit up to two tablespoons of blood into CRO-BIOREP (LU# 204853) for future research purposes. Participants will sign a second informed consent document should they agree to reposit their blood. The research team members and Biorepository staff will each retain a copy of the signed repository informed consent document. It is important to point out that participants do not need to agree to reposit blood in order to participate in the trial.

All patients who agree to reposit blood specimens into CRO-BIOREP (LU# 204853) will be assigned a unique code using our SMART-ID system. This number will be used to connect coded specimens and coded data to other studies conducted by the Clinical Research Office in which they may participate. To receive this number, we will ask participants for sex at birth, month of birth, day of birth, year of birth, and social security number. This information is entered into a secure website where it is hashed into a unique ID using a java script. The participant and research team will receive the unique ID number. Once the number is created, the information that was entered is immediately deleted. This means the website will not retain any of the information that is entered to create the SMART-ID. However, should anyone need to retrieve a SMART-ID number, you will be able to get it again at a later date by going to the website and entering the same information (i.e., sex, date of birth, and social security number) that was entered before.

Freezerworks, the biospecimen tracking software used in the repository, will also automatically assign specimen numbers to incoming specimens. These numbers will identify all donated specimens. The list

that links these codes with patients' identifying information will be kept separate from all research specimens and clinical data.

Information that may readily identify patients will never be shared with anyone.

**v. Study intervention:** Following the clinical practice guidelines of the Endocrine Society, participants in Group 1 will receive 50,000 IU of vitamin D3 once a week for 8 weeks. This dose of vitamin D3 is similar to those used in other breast cancer trials involving women with Stage 0-III disease, and should be sufficient to increase levels in normal weight, overweight and obese women within an 8 week time frame. In addition, weekly dosing will also help to increase study compliance and participants will receive a weekly reminder (phone call, email or text) to take their supplement. Because this is a single arm, open label trial, all participants will be aware that they are taking the study medication and that no placebo is being offered in this trial. Participants will be encouraged to take less than 1000 mg/d of calcium supplementation and to emphasize food sources of calcium (see calcium handout in the appendices). Participants in the non-intervention arm (Group 2) will complete all of the baseline (Week 0) study questionnaires and physical measures.

**vi. Study assessments and activities:** Guided by the Wilson and Cleary health-related QOL model, we will examine seven levels of patient outcomes, including: a) biological and physiological, b) symptom status, c) functional status, d) health perceptions, e) overall QOL, and f) characteristics of the individual and the environment. Variables, measures and times are delineated below (Table 1). Brief details about each of the measurement tools are described below.

Table 1. SAFE-D study variable, measures, constructs and timing				
	Variables	Measures	Wilson & Cleary construct	Week
Aim 1	Low vitamin D (Primary)	25(OH)D, calcium, , serum estradiol, CMP	Biological	0,8
Aim 2	General well-being (Secondary) Pain Fatigue Mood Muscle function Performance status Sleep Overall health QOL	Brief Pain Inventory, FACT-Bone pain Piper Fatigue Scale HADS, PHQ8 Hand grip strength ECOG PSQI Single item question FACT-B, FACT-ES	Symptom status Symptom status Symptom status Functional status Functional status Symptom status Health perceptions Overall QOL	0,4,8 0,4,8 0,4,8 0,8 0 0,4,8 0,4,8 0,8
	Serum vitamin d and Inflammation (Exploratory)	CRP, interleukins, TNF- $\alpha$	Biological	0,8
Other Factors	Demographics and cancer history	Age, race, employment, home life, treatments	Individual, Physiological	0
	Diet	Calcium/Vit D & Fruit, vegetable, fiber screeners	Biological	0
	Obesity	Body composition, Anthropometrics	Physiological	0,8
	Physical activity	Godin	Physiological	0,8
	Support	MOS Social Support	Environmental	0,8
	Sunlight	Sun exposure tool	Physiological	0,8

**vii. Laboratory Outcomes:** Laboratory analyses will be conducted by the Core Laboratory of LUHS, within a Basic Science Laboratory at LUHS and/or by Quest Diagnostics. Serum vitamin D and serum

estradiol will be measured using liquid chromatography/tandem mass spectrometry (LC-MS/MS). This technique is considered the 'gold standard,' providing total 25(OH)D which includes vitamin D2 and vitamin D3, as well as total serum estradiol levels. Calcium will be quantified by spectrophotometry. Biomarkers of inflammation (e.g., C-reactive protein (high sensitivity), interleukins, TNF- $\alpha$ ) will be measured at baseline and follow up with the laboratory analyses conducted in batch to decrease intra-assay variability. The comprehensive metabolic panel (CMP) will be completed to assess baseline organ function, and includes albumin, alkaline phosphatase, ALT, AST, calcium, CO2, BUN/Creatinine, chloride, creatinine with estimated GFR, globulin (calculated), glucose, urea nitrogen, potassium, sodium, total bilirubin, and total protein.

**viii. General well-being outcomes:** To increase comparability across studies, the selected tools have been used previously in breast cancer and/or other cancer populations. (Copies of the tools can be found in the Appendices.)

*Demographics and treatment:* Similar to our previous study, we will obtain information on age, race/ethnicity, employment status, living situation, diagnosis, treatments (medical, surgical and radiation) and metastatic sites.

*Brief Pain Inventory-Short Form:* This validated instrument was designed to assess pain in cancer patients. It includes four items measuring the severity of pain in the last 24 hours on a scale of 0–10, plus seven additional items measuring the extent to which pain interferes with life activities.

*Functional Assessment of Cancer Therapy-Bone Pain (FACT-BP):* This 16-item questionnaire was developed to assess bone pain. It was validated in women with metastatic breast cancer involving the bone. It is scored similarly to other FACT instruments (range 0-4), takes ~5 minutes to complete and has been used in a previous vitamin D supplementation trial for cross-comparison.

*Piper Fatigue Scale (PFS):* The PFS is composed of 22 numerically scaled, "0" to "10" items that measure four dimensions of subjective fatigue: behavioral/severity (6 items); affective meaning (5 items); sensory (5 items); and cognitive/mood (6 items.) Four sub-scale/dimensional scores and total fatigue scores can be calculated to provide reliable, valid assessments of fatigue in breast cancer patients.

*Hospital Anxiety and Depression Scale (HADS):* The HADS is a validated, fourteen item scale with 7 items to categorize anxiety and 7 items to measure depression. Each item on the questionnaire is scored from 0-3, meaning a person can score between 0 and 21 for either anxiety or depression.

*Patient Health Questionnaire 8 (PHQ8):* The PHQ8 is a reliable and valid measure of depression severity. It has 8 questions, each scored 0-3. The sum of all 8 items is used to determine depression, with scores of 10-20 considered major depression and >20 is severe major depression.

*Handgrip strength:* Handgrip strength is measured with a handgrip dynamometer (Jamar) which tests grip strength up to 90 kg. It is often used as a test of skeletal muscle function and correlates with total body muscle strength and mortality.

*Eastern Cooperative Oncology Group Performance Status (ECOG):* This scale is used by clinicians and researchers to assess globally assess disease progress, the impact of the disease on daily living abilities and helps guide appropriate treatment and prognosis. Grades range from 0-5 with scores of 0-2 reflecting full activity to compromises in self-care.

*Pittsburg Sleep Quality Index (PSQI):* This tool contains 19 self-rated questions (7 component scores, ranging from 0-3) and has been validated in a subset of breast cancer patients (Cronbach's alpha 0.8).

In all cases a score of “0” indicates no difficulty, while a score of “3” indicates severe difficulty. The 7 component scores are added to yield a “global” score (range 0-21).

*Overall health:* Using a single item, participants will be asked, “How would you rate your overall health at this time?” This global question format is based on national survey data and scored 1-5 (1=excellent, 2=very good, 3= good, 4=fair and 5=poor.)

*Functional Assessment of Cancer Therapy-Breast and Endocrine Symptoms:* The FACT-B and FACT-ES are widely-used tools that measures multidimensional QOL in patients with breast cancer. They have good reliability, validity and are sensitive to change. There are four QOL subscales: Physical Well-Being, Social/Family Well-Being, Emotional Well-Being, and Functional Well-Being with additional breast cancer and endocrine subscales. Higher scores indicate better QOL and total and subscale scores can be compared to normative scores in breast cancer patients with early and advanced disease.

*Body composition:* This will be assessed using three methods. First, weight, height, waist and hip circumference measures will be taken to calculate body mass index and estimate android and gluteal adiposity. Bioelectrical impedance will be used to assess adiposity at baseline for all participants due to its ease and low costs. Finally, participants will undergo dual energy x-ray absorptiometry (DXA) imaging using the Discovery W by Hologic, located down the hall from the study exam room. This noninvasive, imaging technique provides precise whole-body measurements of fat (total and visceral) and lean tissue, only takes 10 minutes to complete and will be completed on Group 1 participants at their final study visit.

*Dietary intake:* Because dietary sources of vitamin D are restricted to a limited number of foods, precise intakes are easily obtained and quantified with a short measurement tool. The Block Calcium/Vitamin D screener is a brief dietary assessment tool validated and developed from the National Health and Nutrition Examination Survey 1999-2001 dietary recall data. This screener takes 5-7 minutes to complete and includes 19 food items, 3 supplement questions, and adjusts for food fortification practices. To help further characterize dietary intake, participants will also complete the fruit, vegetable and fiber screener. This screener contains 7 questions and takes 3-5 minutes to complete.

*Sun exposure:* Because sunlight constitutes the major source of vitamin D, the adult sun habits questionnaire by Glanz et al will be used. Two questions inquiring about summer sun exposure will be used quantify time spent in the sun, which directly correlates with serum vitamin D levels.

*Godin Exercise Leisure-time Questionnaire:* This 4-item tool allows for the quick quantification of time spent engaged in strenuous, moderate or light activities over a typical 7-day period showing reliability coefficients of 0.8 with  $\dot{V}O_2$  measures. A weekly leisure activity score is generated, as well as the frequency of leisurely activities. This tool is recommended and made available by the NCI.

*Medical Outcomes Study Social Support Survey:* The self-administered survey is a 19-item multi-dimensional scale assessing four aspects of social support: tangible support, affectionate, positive social interaction and emotional/informational support (Cronbach’s alphas >0.9 for all subscales.) Total and subscale scores are obtained and compared, with higher scores indicating more support.

**ix. Study completion:** Participants in the intervention will return to LUMC after 8 weeks of supplementation for their final blood analyses (serum 25(OH)D, calcium, , serum estradiol, inflammatory markers), anthropometric and body composition evaluations, pill counts and questionnaire completion. An 8 week intervention was selected because: 1) this timeframe is consistent with the clinical practice guidelines of the Endocrine Society for vitamin D repletion, and 2) it is an efficient and opportune time to assess the effects of vitamin D on biological and symptom outcomes. Participants in the non-intervention arm will not be followed after their baseline visit. They will be considered “complete” after their baseline visit.

**x. Patient participation and compensation:** We anticipate that we can screen, recruit, and ultimately enroll 50 women over a 12 month time period (n=25 in Group 1, n=25 in Group 2) using patients at LUMC and those referred from RUMC. To enhance retention, participants will be scheduled on a day that is convenient for them and parking tokens will be provided to offset any costs of parking. Honorarium for data collection will be given in a graduated manner [\$20 baseline, \$30 follow up (Group1 only)]. To enhance medication compliance in the intervention arm, participants will be contacted weekly (phone call, text or email) and reminded to take their vitamin D supplements. For persons who drop out, we will assess the reason for study discontinuation and notify their medical oncologists regarding any recent laboratory findings, as appropriate.

